### **2.2.2.4 All bleeds**

“All bleeds” comprise both treated and non-treated bleeds. In this definition, all bleeds are included, irrespective of treatment with coagulation factors, with the following exception: bleeds due to surgery/procedure are excluded, as in the primary analysis.

The 72-hour rule will be applied to the “All bleeds” endpoint. For treated bleeds, it will be implemented exactly as defined in Section 2.2.2.2. For non-treated bleeds (not followed by any treatments with coagulation factors before the recording of a subsequent bleed), it will be implemented by calculating the interval of 72 hours from the bleed itself. Non-Treated bleeds are bleeds not covered by the definition of treated bleeds for the primary endpoint. To clarify, one bleed can be a composition of treated and non-treated bleeds.

Examples:

RE - 2h – T\* – 75h – RE – 2h - T -> 2 bleeds (\*72h calculated from last treatment)

RE\* - 75h – RE – 2h - T -> 2 bleeds (\*72h calculated from bleed because there is no treatment)

RE – 70h – RE – 2h - T -> 1 bleed

RE - 50h – RE – 30h – RE -> 1 bleed

RE – 30h – RE - 25h – LE -> 2 bleeds

RE – 2h – T – 3h – T\* – 35h – RE – 2h – LE\*\* – 45h – LE- 70h - RE -2h -T -> 3 bleeds (\*72h calculated from last treatment, \*\* calculated from previous bleed due to no treatment)

RE=right elbow bleed, LE=left elbow bleed, T=treatment for bleed

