##### **4.5.7.1 Definition of a Bleed**

For the purposes of the efficacy analyses, a standardized definition of bleed, adapted from the standard criteria defined by the FVIII and FIX Subcommittee of the Scientific and Standardization Committee (SSC) of the International Society on Thrombosis and Haemostasis (ISTH), that is similar to the definition used in a recent clinical investigation, will be utilized in this study ([Blanchette et al. 2014](#); [Mahlangu et al. 2014](#)):

- An event is considered a bleed if coagulation factors are administered to treat signs or symptoms of bleeding (pain, swelling, etc.). An additional definition of all reported bleeds (irrespective of treatment with coagulation factors) will be applied for a separate analysis.
- Bleeds starting from the first sign of a bleed and ending 72 hours after the last treatment for the bleed, which have any symptoms of bleeding at the same location or injections are  $\leq 72$  hours apart, are considered the same bleed.
- Any injection to treat the bleed, taken  $> 72$  hours after the preceding injection, is considered the first injection to treat a new bleed at the same location.
- In case of trauma with multiple different locations of bleed, this will be considered as one bleed for the analyses. However, all data will be collected, including the various locations of the different bleeds.
- Any bleed with a different etiology is considered a separate bleed regardless of time from last injection.

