### **2.2.2.2 Treated bleeds**

A bleed is considered to be a “treated bleed” if it is directly followed (i.e., there is not an intervening bleed) by a hemophilia medication reported to be a “Treatment for bleed” (see Haemophilia Medication Record) irrespective of the time between the treatment and the preceding bleed. Note, a bleed occurring at the same time as a treatment, counts as a treated bleed. A bleed and the first treatment thereafter are considered to be pairs (i.e., one treatment belongs to one bleed only), with the following exception: if multiple bleeds occur on the same calendar day, the subsequent treatment is considered to apply for each of these multiple bleeds.

Bleeds due to surgery/procedure will not be included in the primary analysis. In addition, treatments reported as “Treatment for bleed” directly following a bleed due to surgery/procedure are excluded.

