### **2.2.2.3 72-Hour rule**

Two bleeds of the same type (e.g., “joint,” “muscle,” or “other”) and the same etiology and at the same anatomical location are considered to be one bleed if the second occurs within 72 hours from the last treatment for the first bleed. Any bleed with a different etiology is considered a separate bleed regardless of time from last injection. The last treatment is defined as the last treatment before a new bleed occurs, either in the same or in a different location. This is in-line with the above definition that bleeds and treatments are considered to be pairs.

If the bleed location is other/other, other/other is used as the bleed location and not the exact location entered on the separate eCRF page.

In case of trauma with multiple different locations of bleed, this will be considered as one bleed for the analyses. However, all data will be collected, including the various locations of the different bleeds.

A listing of all bleeds is produced. The listing includes all bleed and hemophilia medication, except emicizumab, information entered on the Bleed Record, with an indicator which bleeds are included in the primary analysis and which do not count as separate bleeds due to the 72h rule.

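### Read literally, the all-bleeds 72-hour rule lets an untreated record join two separately treated bleeds, so a patient's all-bleeds count can fall below the treated-bleeds count

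*SAP*

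**What the plan says.** SAP 2.2.2.2 calls a record treated "if it is directly followed (i.e., there is not an intervening bleed) by a hemophilia medication" reported as treatment for a bleed. SAP 2.2.2.3 gives the merging rule: two records of the same type, etiology and location "are considered to be one bleed if the second occurs within 72 hours from the last treatment for the first bleed". It also fixes where that clock starts: "The last treatment is defined as the last treatment before a new bleed occurs, either in the same or in a different location".

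SAP 2.2.2.4 defines all bleeds as treated and non-treated bleeds together, leaving out those due to surgery or a procedure. It keeps the rule above for treated bleeds. For a non-treated bleed, "it will be implemented by calculating the interval of 72 hours from the bleed itself". It adds: "To clarify, one bleed can be a composition of treated and non-treated bleeds". Six worked examples follow. One shows a chain of untreated records: "RE - 50h – RE – 30h – RE -> 1 bleed".

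Protocol 4.5.7.1 ends a bleed 72 hours after its last treatment. An injection given more than 72 hours after the preceding one "is considered the first injection to treat a new bleed at the same location".

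SAP 4.6.1.1 reports an ABR for both endpoints and lists both counts side by side for each patient. Both are also tabulated in categories (4.6.1.2) and by subgroup (4.6.7).

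**The concern.** Under 2.2.2.3 an untreated record has no treatment of its own and so starts no clock. Under 2.2.2.4 it does start one. An untreated record lying between two treatments can therefore link bleeds that the treated-bleeds count keeps apart, and nothing in the SAP prevents this. The endpoint described as treated plus non-treated bleeds can then be smaller than its treated part.

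The all-bleeds ABR would be too low for affected patients, and their listing rows would contradict the endpoint's own description. Two programmers could also resolve the mixed case differently and report different rates.

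**Working it through.** **Rules as coded**
- Each record is paired with the treatments given before the next record at any site (2.2.2.2, 2.2.2.3).
- A record joins the earlier bleed at its site if it starts no more than 72 h after the anchor. The anchor is the last treatment of the earlier record if that record was treated, otherwise the earlier record itself (2.2.2.4).
- The treated count drops untreated records first. SAP 2.2.2.7 and 2.2.2.9 state this order for treated joint and treated spontaneous bleeds. For treated bleeds overall it is inferred from the clock running from treatment.

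**Reproducing the SAP.** The literal all-bleeds rule returns 2, 2, 1, 1, 2, 3 for the six examples, which matches every printed count. In the fourth example the third record is 50 + 30 = 80 h after the first but 30 h after the second, and the count is 1. So the clock does restart at an untreated record.

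**The uncovered sequence** (same site, type and etiology)

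| Record | Treated at | From last treatment | From previous record |
|---|---|---|---|
| 0 h | 2 h | – | – |
| 35 h | none | 33 h | 35 h |
| 100 h | 102 h | 98 h | 65 h |

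- Treated bleeds: 98 h > 72 h, so the count is 2.
- All bleeds: 33 h ≤ 72 h joins the second record to the first, and 65 h ≤ 72 h joins the third to the second. The count is 1.
- Protocol: the second injection comes 102 − 2 = 100 h after the first, so it opens a new bleed.
- Calculated ABR over 730.5 days: treated 2/730.5 × 365.25 = 1.0; all 1/730.5 × 365.25 = 0.5.

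The chain has no limit. Records at 0 (treated), 60, 120, 180 (treated), 240 and 300 h (treated) give 3 treated bleeds and 1 all-bleed.

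**When it happens.** With one untreated record between two treated ones, let *a* be the gap from the treatment to the untreated record and *b* the gap from there to the next treated record. The counts invert exactly when a ≤ 72, b ≤ 72 and a + b > 72. Of the 72 × 72 = 5,184 whole-hour pairs with both gaps from 1 to 72 h, 2,628 meet this. That is a share of possible timings, not an expected frequency.

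**Size, on stated assumptions.** The documents do not say how often patients record again at one site. Assume gaps spread evenly over 12–72 h, treatment 2 h after a treated record, and 53% of records treated. The 53% is 2.9/5.5, the HAVEN 1 treated-bleeds ABR over the all-bleeds ABR (protocol 1.2.2.3), used as a proxy. The shortfall below is the treated bleeds lost, as a share of the literal all-bleeds total.

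| Probability of a further record | Episodes with treated > all | Shortfall in all-bleeds total |
|---|---|---|
| 0.2 | 0.5% | about 0.5% |
| 0.4 | about 3% | about 3% |
| 0.6 | 10.5% | about 12% |

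**The case against.** The strongest reply is that the mixed case is unclear rather than wrongly fixed. No printed example has the treated, untreated, treated sequence. In the sixth, the last right-elbow record comes 35 + 2 + 45 + 70 = 152 h after the treatment and 117 h after the untreated right-elbow record, so it decides nothing. The SAP also says treated bleeds follow the primary definition exactly. Holding the clock at an episode's last treatment reproduces all six counts with no inversion. That much stands. But this reading does not fit the sentence that starts an untreated record's 72 hours at the record itself, and an ambiguity that changes a reported rate still needs settling.

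A second reply is that the merging is deliberate and that an untreated record between two treatments may be one continuing episode. Chaining of untreated records is plainly intended. Joining bleeds that the protocol and 2.2.2.3 separate is not stated as an aim.

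Third, SAP 4.6.6 includes a sensitivity analysis without the 72-hour rule, and the listings would expose an inversion. Both help detection. Neither corrects the main all-bleeds ABR.

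A reader might infer that the all-bleeds rate is understated by half, or mainly in patients whose bleeding is worst controlled. The documents support neither. The halving applies only within an inverted episode of the simplest kind. Bridging does need repeated records at one site, but no data here link that to poor control.

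**Conclusion.** The point holds as a defect in the written rule: applied literally, 2.2.2.4 can give fewer all-bleeds than treated bleeds. Its practical size is unknown. The range of about 0.5% to 12% rests on re-recording probabilities with no source in the documents and on a ratio of model-based ABRs standing in for the share of records treated.

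The reach is limited. The main bleed analysis uses treated bleeds and does not change. Whole-period zero-bleed proportions do not change either, because a patient with any treated bleed still has at least one all-bleed. What can change is the all-bleeds count, its ABR and its ABR categories. Efficacy is a secondary objective here and all analyses are descriptive, so this should be corrected but does not threaten the study's main conclusion.

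**What to change.** In SAP 2.2.2.4, form treated bleeds first by the 2.2.2.3 rule. Then attach or chain untreated records within 72 h, but never let an untreated record join two treated bleeds that 2.2.2.3 counts separately. Say in 2.2.2.3 that untreated records are set aside before treated bleeds are counted, as 2.2.2.7 and 2.2.2.9 already do for their endpoints. Add the 0 h, 35 h, 100 h sequence as a worked example (treated 2, all 2), and program a check that all bleeds are at least treated bleeds for every patient. The same edit can correct the cross-reference in 2.2.2.4, which points to 2.2.2.2 although the 72-hour rule is in 2.2.2.3.

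The six printed examples keep their counts of 2, 2, 1, 1, 2, 3. The cost is a few lines of text and a small change to one derivation. No new data are needed. The downside is a slightly higher, and so less favourable, all-bleeds ABR.

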### 2.2.2.5 Bleed Sites

The bleed sites are defined as follows:

- Joint bleeds, which are defined as having an unusual sensation (“aura”) in the joint in combination with any of the following:
  - Increasing swelling or warmth of the skin over the joint
  - Increasing pain
  - Progressive loss of range of motion or difficulty in using the limb as compared with baseline.
- Muscle bleeds
- Other bleeds.

### 2.2.2.6 Definitions of Cause/Classification of Bleeds

Bleed assessments will be separated into spontaneous bleeds, traumatic bleeds, and bleeds related to procedures. Both spontaneous bleeds (i.e., the occurrence of hemorrhage where neither the patient nor a caregiver can identify a reason) and traumatic bleeds (i.e., hemorrhage occurring secondary to an event such as trauma, “strenuous” activity, or “overuse”) will be collected. The definitions for the different type of bleeds are as follows:

- **Spontaneous bleeds.** Bleeds will be classified as spontaneous if a patient records a bleed when there is no known contributing factor such as definite trauma, antecedent “strenuous” activity, “overuse”, or procedure/surgery. The determination of what constitutes “strenuous” or “overuse” will be at the discretion of the patient. For example, light jogging may be considered “non-strenuous” while sprinting may be considered “strenuous”; lifting of weights for a short period of time may be considered “moderate use” while repetitive weightlifting may be considered “overuse”.
- **Traumatic bleeds.** Bleeds should be classified as traumatic if a patient records a bleed when there is a known or believed reason for the bleed. For example, if a patient were to exercise “strenuously” and then have a bleed in the absence of any

obvious injury, the bleed would be recorded as a traumatic bleed because, although no injury occurred, there was antecedent “strenuous” activity. Bleeds with preceding injuries would certainly be classified as traumatic. In addition, bleeds related to surgery, such as hematomas resulting from any surgeries, will also be classified as traumatic bleeds. Bleeds related to surgeries will not be associated with any trauma except surgery-induced trauma.

- **Bleeds related to procedures.** This category would include hematomas resulting from any invasive procedure (e.g., tooth extractions, venipuncture, or SC drug administrations) or invasive diagnostic procedures (e.g., lumbar puncture, arterial blood gas determination, or any endoscopy with biopsy, etc.) or surgeries. Any instances of these bleeds would not be counted as bleeds in the context of the study, but the relevant data will be collected. Bleeds related to procedures will not be associated with any trauma except procedure-induced trauma.

### **2.2.2.7 Treated Joint Bleeds**

Joint bleeds are defined as bleeds where the bleed type is “joint” and at least one of the following symptoms has been observed: increased swelling or warmth of the skin over the joint, increased pain in the joint or decreased range of motion, or difficulty moving the joint compared to baseline.

For the analysis, all treated bleeds that fulfill the above joint bleeds definition will be included and then the 72-hour rule will be applied. Bleeds due to procedure/surgery will be excluded.

In case multiple bleeds are counted as one bleed (72h rule), all of these bleeds needs to fulfill the above rule.

Additional analyses will be performed for joint bleeds where the bleed site is “joint”, regardless of any accompanying reported symptom.

### **2.2.2.8 Treated Target Joint Bleeds**

Target joints are major joints in which repeated bleeds occur (i.e.,  $\geq 3$  bleeds in the same joint over the last 24 weeks prior to study entry). The target joints prior to study entry are identified through the eCRF. The bleeds in target joints during the efficacy period (see Section 4.1) are defined by first selecting the bleeds that fulfill the definition of a treated joint bleed (see Section 2.2.2.7) and then counting how many of these occurred in a target joint prior to study entry. The locations to be taken into account are: shoulder, elbow, wrist, fingers/thumb, hip, knee, ankle, sole/heel, and toes. Left and right side of the same joint type are considered to be separate joints.

### **2.2.2.9 Treated Spontaneous Bleeds**

For the analysis all treated bleeds that fulfil the above spontaneous bleeds definition (section 2.2.2.6) will be included and then the 72-hour rule will be applied.

## **2.2.3 HRQoL Assessments**

The Haem-A-QoL (version AU 3.0; UK English) and the Hemophilia Quality of Life Short Form (Haemo-QoL-SF) (version AU 2.0; UK English) will be completed electronically and

used to measure HRQoL in adults and adolescents, respectively. Paper versions of the questionnaires are also available in case of ePRO outage or if an ePRO device is otherwise unavailable.

The Haem-A-QoL was designed for adult patients with hemophilia. It consists of 46 items comprising 10 dimensions (physical health, feelings, view of yourself, sports and leisure, work and school, dealing with hemophilia, treatment, future, family planning, and partnerships and sexuality) and a scale representing total score. Items are rated according to five response options, although for some items there is also a 'not applicable' option (Mackensen and Gringeri 2010; Wyrwich et al. 2015).

The Haemo-QoL has been developed as a series of age-related questionnaires to measure HRQoL in children and adolescents with hemophilia (Bullinger et al. 2002; Pollak et al. 2006; Von Mackensen and Bullinger 2004). These questionnaires include a 77-item long form, a 35-item short form, and an 8-item index form. Long versions for three different age groups contain 21–77 items and cover 8–12 dimensions of HRQoL. Furthermore, two age-specific short form measures containing 16 and 35 items have been developed. The short version for older children (8–16 years) containing 35 items was selected for this study. This version covers nine dimensions considered relevant for the children's HRQoL (physical health, feelings, view of yourself, family, friends, other people, sports, dealing with hemophilia, and treatment). Items are rated with respect to five response options: never, rarely, sometimes, often, and all the time.

#### **2.2.4 Health Status Assessments (EQ-5D-5L)**

The EQ-5D-5L (version 2; UK English) is a generic, self-report, preference-based health utility measure that consists of six questions that are completed electronically and is used to assess health status and inform pharmacoeconomic evaluations. Paper versions of the questionnaires are also available in case of ePRO outage or if an ePRO device is otherwise unavailable. The EQ-5D-5L consists of two components. The first part, health state classification, contains five dimensions of health: mobility, self-care, usual activities, pain / discomfort, and anxiety / depression (Herdman et al. 2011; Janssen et al. 2013). Published weights are available that permit the creation of a single summary score. Overall scores range from 0 to 1, with low scores representing a higher level of dysfunction. The second part is a 0 to 100-point visual analog scale (VAS), which assesses current health status and higher scores are reflective of better health.

#### **2.2.5 Treatment Preference Questionnaire**

Patient preference will be assessed through a paper version of the EmiPref questionnaire (see Protocol Appendix 3), which asks patients to specify the treatment they would prefer to continue to receive after receiving treatment with their previous episodic or prophylactic regimen and SC emicizumab. Patients who express a preference are then asked to identify the reasons which may have influenced their decision and indicate the top three reasons for their choice. Patients will complete this questionnaire after 3 months of treatment with emicizumab.

### **2.3 DETERMINATION OF SAMPLE SIZE**

A sample size of approximately 200 patients is planned for this study.

For the purpose of the sample size calculation, the incidence of adverse events was chosen as the safety endpoint of primary interest.

If the observed incidence of adverse events is between 2.5% and 15%, the precision for the estimated incidence rate is presented below according to the 95% Clopper-Pearson confidence intervals (CIs) (Table 1).

**Table 1: Clopper-Pearson 95% CIs for the Incidence of AEs (Based on N=200)**

Number of AE Events (Observed AE Incidence)	95% Clopper-Pearson CIs
5 (2.5%)	0.8%–5.7%
10 (5.0%)	2.4%–9.0%
20 (10.0%)	6.2%–15.0%
30 (15.0%)	10.4%–20.7%

### **2.4 ANALYSIS TIMING**

The first interim analysis will be performed once approximately 100 patients have received treatment with emicizumab for at least 24 weeks.

A second interim analysis will be performed when approximately 100 patients have received treatment with emicizumab for at least 52 weeks.

The data from these analyses will subsequently be presented to the independent Data Monitoring Committee (iDMC) in order to enable them to effectively monitor the study (see Section 3.3).

Given the hypothesis-generating nature of this study, the Sponsor may choose to conduct up to two additional interim efficacy analyses (i.e., beyond what is specified in Section 6.9.1 of the clinical study protocol [CSP]).

The final analysis will be conducted when all patients have completed 2 years of treatment or have withdrawn, whichever occurs sooner.

## **3. STUDY CONDUCT**

The study conduct is described in Section 2.

### **3.1 RANDOMISATION ISSUES**

Not applicable

### **3.2 INDEPENDENT REVIEW FACILITY**

Not applicable

### **3.3 DATA MONITORING**

The iDMC will review safety data on a regular basis until all patients have been enrolled and have completed treatment. All analyses for review by the iDMC will be prepared by the study statistician. Analyses of safety events will be conducted after approximately 100 patients have completed 24 weeks in the study and again after approximately 100 patients have completed 52 weeks in the study. Thereafter, the iDMC will meet at a frequency determined by the iDMC and the Sponsor according to the emerging safety profile.

Further details are specified in a separate iDMC charter.

## **4. STATISTICAL METHODS**

No formal statistical hypothesis tests will be performed and all analyses are considered descriptive.

Categorical data will be summarized using frequencies and percentages (including a category for missing, if appropriate). Continuous data will be summarized using descriptive statistics (N, mean, standard deviation, median, lower quartile, upper quartile, minimum and maximum). Other analysis methods will be specified (below) where applicable.

### **4.1 REPORTING PERIODS**

The following definitions are used to allocate data to study periods. The same definitions are used for all outputs, e.g. AEs, laboratory data, patient disposition, efficacy and quality of life, unless otherwise specified.

